*** Describe the circumstances and any procedures for orderly termination:**

It is possible that individuals may be removed from participation due to a change in their diagnosis or a change in their treatment plan is recommended.

8. Describe procedures that will be followed when subjects withdraw from the research, including partial withdrawal from procedures with continued data collection and data already collected:

Depending on the circumstances, individuals may be removed from participation and directed to alternative methods of treatment if warranted.

Conflict of Interest

1. * **Is this an FDA Covered Clinical Study?**

Yes No

Answer **YES** if it is:

- A study of a drug or device in humans to be submitted in a marketing application or reclassification petition that the applicant or FDA relies on to establish that the product is effective (including studies that show equivalence to an effective product); or
- A study in which a single investigator makes a significant contribution to the demonstration of safety.

Do **NOT** include:

- phase I tolerance studies or pharmacokinetic studies;
- clinical pharmacology studies (unless they are critical to an efficacy determination);
- large open safety studies conducted at multiple sites;
- treatment protocols; or
- parallel track protocols.

2. * **Does this study involve a Non-Significant Risk Device and you anticipate including the results as part of any type of submission to the FDA for approval of this device?**

Yes No

3. * **Is this study funded in part or whole by a PHS Agency?**

Yes No

4. * **Does any investigator involved in this study (select all that apply):**

- A. Have a financial interest (aggregated value of equity and remuneration during the past or next twelve months) in a publicly-traded entity that either sponsors this research or owns the technology being evaluated or developed that exceeds a 5% ownership interest or a current value of \$10,000?
- B. Receive remuneration (during the past or next twelve months) from a non-publicly traded entity that either sponsors this research or owns the technology being evaluated or developed that exceeds \$10,000?
- C. Have equity in a non-publicly traded entity that either sponsors this research or owns the technology being evaluated or developed?

- D. Have rights as either the author or inventor of intellectual property being evaluated or developed in this research and for which you are receiving royalties, milestone fees, or other proceeds that have or will exceed \$10,000 in any 12-month period (include payments through the University of Pittsburgh, the Veterans Administration Pittsburgh Healthcare System, UPMC, and University of Pittsburgh Physicians)?
-
- E. Have an officer or management position with a company that either sponsors this research or owns the technology being evaluated or developed?
-
- F. Receive compensation of any amount when the value of the compensation would be affected by the outcome of this research, such as compensation that is explicitly greater for a favorable outcome than for an unfavorable outcome or compensation in the form of an equity interest in the entity that either sponsors this research or owns the technology being evaluated or developed?
-
- None of the above options apply and there are no other financial conflicts of interest in the conduct of this research.

5. **Provide the name of the investigator(s) and describe the nature of the Significant Financial Interest(s):**

Ancillary Reviews

1. **Ancillary reviews or notifications selected below are required based on previous answers to questions. If a selection is incorrect, return to the appropriate page and adjust the answers to questions on that page:**

- Conflict of Interest (**COI**)
- Clinical and Translational Research Center (**CTRRC**)
- Data Security
- Honest Broker
- UPMC Investigational Drug Service
- Pitt Medical School Review
- Pitt+Me
- Office of Investigator-Sponsored IND & IDE Support (**O3IS**)
- Radioactive Drug Research Committee (**RDRC**)(study involves the evaluation or use of procedures that emit ionizing radiation)
- ORP Business **Manager** (required for industry sponsored studies)
- Religious Directives
- Scientific Review
- Health Record Research Request (**R3**) (required if using UPMC clinical data and authorization for other UPMC data sources for research)
- UPMC Office of Sponsored Programs and Research **Support** (using UPMC facilities and/or UPMC patients during the conduct of the study)

2. **Additional ancillary reviews the PI may choose to include as needed for the research:**

- Human Stem Cell Oversight (**hSCRO**)
- Institutional Biosafety Committee (**IBC**)(study involves deliberate transfer of recombinant or synthetic nucleic acid molecules)

Good Clinical Practice (GCP) Training

1. * **Regardless of funding source, is this study a clinical trial (as defined by the NIH)?**

Yes No

ClinicalTrials.gov Information

Visit the University of Pittsburgh Office for ClinicalTrials.gov website or contact [contact] for further information.

2. * **Was this study registered, or will it be registered, on ClinicalTrials.gov?**

Yes No

3. * **Is the University of Pittsburgh or UPMC the Sponsor Organization for this study record?**

Yes No

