*** Will you be recruiting individuals for participation in this study?**

Yes No

1. * Describe who will be recruiting individuals for participation for this study:

Study team members also involved in clinical care.

2. * Select all methods to be used for recruitment:

Directly approaching potential subjects (in-person)

3. * Provide details on your recruitment methods:

Individuals will be identified during the course of usual clinical care of patients at the University of Pittsburgh Voice Center. As potential subjects are being clinically evaluated in the University of Pittsburgh Voice Center, they will encounter at least one member of the research team who will be able to determine eligibility through the clinical review of medical records associated with their visit. Once verification of eligibility is obtained, potential subjects will be approached by a member of the research team to review the informed consent document. Any and all questions will be addressed during this time.

4. * Describe all compensation/incentives offered to participants and timing of these offers:

Participants will be paid \$100 in total for completion of the 4 voice therapy sessions and follow-up session. The \$100 payment will be made after the completion of the 5 visits (4 therapy and 1 follow up). There will be no partial payment. Payment will be managed with a reloadable debit card.

Participants will be paid when they present for the follow-up visit after completing 4 voice therapy sessions.

5. Recruitment materials: (attach all material to be seen or heard by subjects, including advertisements and scripts)

Document Category Date Modified Document History

There are no items to display

Study Aims

1. * Describe the purpose, specific aims, or objectives and state the hypotheses to be tested:

To determine the efficacy of a semi-occluded mask in the treatment of patients with voice disorders

To determine initial efficacy of a semi-occluded facemask on voice outcomes in patients with MTD, lesions, and atrophy. We hypothesize that patients will demonstrate an improvement in acoustic, aerodynamic outcomes, and voice handicap index scores following therapy.

2. * Describe the relevant prior experience and gaps in current knowledge including preliminary data. Provide for the scientific or scholarly background for, rationale for, and significance of the research based on existing literature and how it will add to existing knowledge:

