	Other Risks	-emotional discomfort/uncomfortable feeling (as stated in consent) -potential for skin irritation due to allergy or mild contact pressure

View	Research Activity	voice therapy session
	Common Risks	No Value Entered
	Infrequent Risks	No Value Entered
	Other Risks	rare risk of worsening voice problem

2. * Describe the steps that will be taken to prevent or to minimize risks:

Confidentiality will be maintained as per the usual methods in the Dept. of Otolaryngology. All electronic subject information will be stored on password protected, restricted access servers. Any paper documentation will be maintained in locked file cabinets within the locked offices of the Department of Otolaryngology.

Though uncommon, it is possible that a patient participant's voice could worsen during a voice therapy session. If this occurs, the voice therapist will give the participant the option of discontinuing voice therapy and can refer the patient back to the treating otolaryngologist for repeat vocal fold examination if so desired.

Wearing of the partially occluded mask could potentially be uncomfortable, emotionally for some individuals. The mask is not "fixed" to the individual's face, and can be removed by the subject at any time. The subject is in control of holding the mask over their nose and mouth. In the event of skin allergy/irritation, mask use may need to be discontinued.

3. Financial risks - will the subject or insurer be charged for any research required procedures?

Yes No

4. Describe the steps that will be taken to protect subjects' privacy:

All study related procedures will be performed in private rooms as is typical of the usual clinical care associated with the diagnosis and treatment of the qualifying voice disorders. Information being collected will be limited to the minimum necessary to achieve the specific aims in this study and to lay the groundwork for future research in this area.

5. What steps will be taken in the event that a clinically significant, unexpected disease or condition is identified during the conduct of the study:

All participants will be under the clinical care of physicians in the Department of Otolaryngology. Usual clinical practice procedures will be maintained.

6. Describe the potential benefit that individual subjects may experience from taking part in the research or indicate if there is no direct benefit. Do not include benefits to society or others:

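### No VHI-10 is scheduled for participants who stop early, so they may be missing from the only planned test; the likely bias is small, but the plan cannot show its size or direction

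*Combined protocol and SAP*

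**What the plan says.** - **Measurement.** Research Activities, item 1, lists VHI-10 at baseline (from the medical record) and at follow-up. It lists no other collection after baseline. The same item describes four therapy sessions and a follow-up visit at one week.
- **Payment.** Recruitment Methods, item 4, ties that visit to completion: "Participants will be paid when they present for the follow-up visit after completing 4 voice therapy sessions". The $100 is paid only after all five visits.
- **Routes out.** Risk and Benefits, item 2, allows that a participant's "voice could worsen during a voice therapy session", in which case "the voice therapist will give the participant the option of discontinuing voice therapy". The risk list in item 1 calls this a "rare risk of worsening voice problem". Item 2 adds: "In the event of skin allergy/irritation, mask use may need to be discontinued". Under item 7, "individuals may be removed from participation due to a change in their diagnosis or a change in their treatment plan is recommended".
- **Withdrawal.** Risk and Benefits, item 8, asks for the procedures on withdrawal, "including partial withdrawal from procedures with continued data collection and data already collected". The whole answer is: "Depending on the circumstances, individuals may be removed from participation and directed to alternative methods of treatment if warranted".
- **Analysis.** Study Design, item 8, names one test, a paired t-test of VHI-10 against baseline, with a target of 20. Item 1 of that section gives 30. No analysis set, missing-data rule or allowance for loss is stated.
- **Other source of scores.** Medical Records, item 1, allows VHI-10 scores to be taken from the medical record.

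**The concern.** A paired t-test can use only people who have both scores. The plan foresees early stopping but schedules no VHI-10 for those who stop, and all-or-nothing payment gives them no financial reason to return. The form asks about continued data collection after withdrawal, and the answer does not address it.

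The study has one group, so the mean change is the whole efficacy result, and no comparison arm could show a similar loss. If people who are doing worse tend to leave, the mean among those remaining is too favourable. If people who are doing better leave, it is too unfavourable. If leaving has nothing to do with VHI-10 change, as may be so for skin irritation, there is no bias. Without scores from those who left, the investigators could not tell afterwards which case they were in.

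**Working it through.** The plan states no power, SD, effect size, significance level or loss rate, so there is no figure of its own to reproduce. What follows illustrates size under declared assumptions.

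**Inputs.** From the documents: N = 20 (Study Design, item 8) or N = 30 (Study Design, item 1), and a paired t-test. Assumed: two-sided 5% level, so 2.5% in the improvement direction; zero true mean change; the loss rate; and how strongly leaving depends on change.

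**Step 1: the bias.** Let d be the share without a follow-up score.

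bias in mean change = d × (mean change in completers − mean change in stoppers)

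With a gap of 1 SD, d = 10%, 20% and 30% give 0.10, 0.20 and 0.30 SD. With a gap of −1 SD the signs reverse. With no gap the bias is zero.

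**Step 2: false improvement.** Change ~ N(0,1), positive meaning improvement; logit P(leave) = logit(p0) − b × change; b = 0.5 is weak and b = 1 moderate dependence. There were 200,000 simulated trials per scenario, analysed in completers.

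| p0, b | Loss | Bias (SD) | False improvement, N = 20 | N = 30 |
|---|---|---|---|---|
| b = 0 | – | 0 | 2.5% | – |
| 0.05, 0.5 | 5.5% | +0.028 | 3.3% | 3.5% |
| 0.10, 0.5 | 10.9% | +0.054 | 4.1% | – |
| 0.10, 1 | 13.4% | +0.120 | 6.9% | – |
| 0.20, 1 | 23.9% | +0.205 | 11.9% | 16.6% |
| 0.05, −0.5 | – | −0.027 | 1.9% | 1.8% |
| 0.20, −1 | – | −0.204 | 0.3% | 0.2% |

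At N = 20, 5.5% is 0.055 × 20 = 1.1 people and 23.9% is 0.239 × 20 = 4.8 people.

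**Step 3: cross-check.** By Step 1 the implied gaps are 0.028/0.055 = 0.51 SD at the low end and 0.205/0.239 = 0.86 SD at the high end. A noncentral-t calculation with 20 enrolled, 20% loss (16 pairs) and a 1 SD gap gives a bias of 0.20 SD and 11.6% rejection, both directions counted, against 5%. The size agrees with the high-end row.

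**Step 4: which row do the documents point to?** The only exit explicitly tied to outcome is worsening within a session, which is called rare. That fits the 5.5% row. Nothing supports or excludes the 23.9% row.

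**Step 5: would collecting scores help?** At the high end (N = 20), recovering unaffected follow-up scores from a random 50%, 80% or 100% of leavers lowers false improvement from 11.9% to 5.4%, 3.5% and 2.5%. If every leaver's score is recovered but each has gained 0.5 or 1.0 SD from redirected treatment, the figure is 7.6% or 18.8%. So it must be recorded whether other treatment had started.

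**Step 6: why not simply assume leavers got worse?** Take a true change of 0.8 SD and 20% loss unrelated to change. Setting leavers to 1 SD of worsening shifts the mean by 0.20 × (−1 − 0.8) = −0.36 SD and cuts power from about 84% to 38%. A sensitivity analysis in the worsening direction alone can hide a real effect.

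**The case against.** **Are early stoppers excluded automatically?** A reader might infer this, but the documents do not say it. Follow-up is tied to four completed sessions in a payment clause; the data list in Research Activities carries no such condition. Risk and Benefits, item 2, speaks of stopping therapy or the mask, not of leaving the study. Item 8 says removal may happen, depending on circumstances. Participants stay under the department's clinical care (Risk and Benefits, item 5), and VHI-10 may be read from the record. All of this stands, so the point is that their scores may be missing, not that they must be. Even so, no score is scheduled and no rule brings a record value into the test.

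**The consent form is not available.** It may say something about data after withdrawal. That stands as a caveat on item 8, but it does not fill the gap in the data schedule or the analysis.

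**The documents point only to a small effect.** This also stands. In an uncontrolled pilot, 0.03 SD matters less than the absence of a comparator. It limits the importance of the point without answering it: the stated aim is efficacy, a significance test is planned, and one added invitation is cheap.

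**It may be too late.** Study Design, item 4, estimates completion by 12/31/2019 and the document is dated February 11, 2020. Enrolment status is not given. If visits are finished, the record search and the reporting can still be done.

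**Conclusion.** The point holds and should be acted on, at moderate weight. The plan schedules no VHI-10 for participants who stop early, although it foresees stopping, and anyone without a follow-up score is absent from the only planned test.

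The likely effect is small: about +0.03 SD, and 3.3% false improvement against 2.5%, at about 5% loss with N = 20, zero true change and weak dependence. A reader might take the 12% (N = 20) or 17% (N = 30) figures as the expected inflation. The documents do not support that, because those figures need 24% loss and moderate dependence, both assumed. Nor do the documents show that the result must be flattered. The named outcome-linked route points that way, but other routes may carry no bias, and a reversed bias is possible.

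**What to change.** Amend Research Activities, item 1, and Risk and Benefits, item 8 (and Electronic Data Management, item 4, if phone collection requires it):

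1. Invite every participant who began therapy and has not withdrawn consent to complete the follow-up VHI-10 when that visit would have fallen, whether or not four sessions were completed. Collect it in clinic, by phone or from the medical record, and note whether other treatment had started.
2. Make the primary analysis set all who began therapy and have a follow-up score. Report completers alongside.
3. Report the number of early stops, by reason.
4. For scores still missing, give one tipping-point analysis in both directions. Let those without scores differ from completers by a range of values, better and worse (for example −1 to +1 observed SD), and report the value at which the conclusion changes.

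If visits are already finished, search the records for step 1 and carry out steps 2 to 4.

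The cost is one amendment, one 10-item questionnaire per early stopper and a short table. Phone scores may differ in mode from clinic scores, some scores will reflect other treatment, and the estimate may be smaller. No rule on stopping, removal or redirection is changed.

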*** Who will be the Responsible Party for this study record?**

Principal Investigator of this IRB application

Supporting Documents

 **Attach any additional supporting documents not previously uploaded. Name the documents as you want them to appear in the approval letter:**

Document	Category	Date Modified	Document History
View Data Safety and Monitoring Report-PittPRO conversion 2019.docx(0.01)	Other	2/8/2019	History

Add Storage Information

1. * **Select a Storage Type:**

UPMC owned desktop, laptop or other device

2. **Description:**

3. * **Will identifiable data be stored in this location?**

Yes No

4. * **Will sensitive data be stored in this location?**

Yes No

5. **Will de-Identified or anonymous data be stored in this location?**

Yes No

6. * **Is anti-virus software installed and up to date on all devices and are the operating systems kept up-to-date on all devices?**

Yes No

7. **Provide additional information as needed:**

Add Storage Information

1. * **Select a Storage Type:**

Server: UPMC Managed Server

2. **Description:**

3. * **Will identifiable data be stored in this location?**

Yes No

4. * **Will sensitive data be stored in this location?**

Yes No

5. **Will de-identified or anonymous data be stored in this location?**

Yes No

6. **Provide additional information as needed:**

Risk

1. *** Research Activity:**
medical record review

2. **Common Risks:**

3. **Infrequent Risks:**

4. **Other Risks:**
rare risk of breach of confidentiality

Risk

1. * Research Activity:

wearing partially occluded mask

2. Common Risks:

3. Infrequent Risks:

4. Other Risks:

-emotional discomfort/uncomfortable feeling (as stated in consent) -potential for skin irritation due to allergy or mild contact pressure

Risk

1. * Research Activity:

voice therapy session

2. Common Risks:

3. Infrequent Risks:

4. Other Risks:

rare risk of worsening voice problem
